7.1.2. Secondary Efficacy Assessments

Time to complete wound closure

The time (in days) from first treatment at baseline of the ulcer until it closes completely will be recorded.

Change in wound size over time

Ulcer size over time will be assessed from the digital photographs of the ulcer taken at each visit.

Incidence of recurrence

Recurrence is identified as an interruption in the epithelium following complete healing of the index ulcer. If the subject does have a recurrence, this will be documented and the re-opened ulcer will be measured and recorded

Incidence of Amputation

All amputations will be recorded. The investigator will judge whether the amputation was done because of the index ulcer or for different reasons.

Incidence of adverse events and device effects

Quality of Life

Pain - A Visual Analogue Scale will be used to determine pain levels.

Mood and Function - The Cardiff Wound Impact Schedule (CWIS) assesses levels of mood and function and is the tool used to determine Quality of Life (Appendix I). (Subjects in countries where the CWIS has not been validated will be debriefed on its use at the end of the study).

Economic Analysis

Economic assessments will be determined from the Euroqol-5D (EQ-5D), subject diary and

medical records documenting dressing changes, time, location and healthcare professional assistance and management (Appendix I).

Cost effectiveness will be determined by examining the difference in the number of healed ulcers in relation to the difference in cost in each randomized group

Incremental cost per additional ulcer healed=
$$\frac{\text{Cost of treatment (TWO) - Cost treatment (Control)}}{\text{Healed ulcers (TWO) - Healed ulcers (Control)}}$$

Cost Utility will be determined by examining the difference in Quality Adjusted Life Years (QALYs) associated with the different treatment regimens and their associated costs. Health utilities will be derived from the EQ-5D tool and used to calculate QALYs in each group. This will be related to overall treatment costs using the following formula

Incremental cost per QALY =
$$\frac{\text{Cost of treatment (TWO)-cost of treatment (control)}}{\text{QALY (TWO) - QALY(control)}}$$

See 7.2 Safety Endpoints

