The subject is supplied with the off-loading boot/CROW boot and treated with the dressings defined for this study for 2 weeks until the baseline assessment takes place.

8.2.2. *Baseline Procedures (after 2 week run-in period)*

Prospective subjects must meet all inclusion criteria to be eligible to participate in the study. Missing data for the final verification of all inclusion and exclusion criteria will be performed including HbA1c which has to be available at the baseline visit.

The following data will be collected at the baseline visit prior to randomization treatment with the TWO₂ therapy or Control therapy:

- 1) Verify Informed Consent
- 2) Record adverse events
- 3) Record changes in concomitant medication
- 4) Verify subject eligibility by checking against inclusion/exclusion criteria
- 5) Quality of Life Assessment using CWIS
- 6) Collect diary card/Compliance assessment (treatment/dressings)
- 7) Remove dressings/wound cleansing
- 8) Pain Assessment using the Visual Numerical Rating Scale
- 9) Digital photograph (post debridement)
- 10) Debridement if needed
- 11) Wound assessment: Location, size and appearance
- 12) Infection assessment
- 13) Dress wound with study dressings
- 14) Record lab data if not previously recorded
- 15) Education on diabetes management and foot care and off-loading boot/CROW boot
- 16) Dispense study dressings and diary card
- 17) Health Economic Assessment (including EQ-5D)
- 18) Punch biopsies
- 19) Device competency assessment (Completed in subjects home or equivalent after baseline clinic visit)

8.2.3. *Randomization Procedures*

Subjects will be randomized to receive either TWO₂ therapy as an adjunctive therapy or a control therapy.

8.2.4. *Weekly procedures during treatment period*

All subjects (TWO₂ therapy and control therapy) will have a weekly assessment in the clinic until the index ulcer is closed or 12 weeks have passed – whichever is sooner.

Each Assessment Visit will include the following procedures:

- 1) Verify Informed Consent
- 2) Record adverse events/device effects
- 3) Record changes in concomitant medication
- 4) Quality of Life assessment using CWIS (week 12 only)
- 5) Collect diary card/Compliance assessment (treatment/dressings)
- 6) Remove dressings/wound cleansing
- 7) Pain Assessment using the Visual Numerical Rating Scale
- 8) Digital photograph (post debridement)
- 9) Debridement if needed
- 10) Wound assessment: Location, size, depth and appearance
- 11) Infection assessment

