- 12) Blood sample taken to obtain values for (**visit 12 only**):
 - Electrolytes
 - Creatinine
 - HbA1c, blood glucose
 - WBC
 - Albumin and pre-albumin (where available)
 - CBC
 - C-reactive protein
- 13) EQ-5D) (week 4, 8 and 12 only)
- 14) Education on diabetes management and foot care and off-loading boot/CROW boot
- 15) Dispense study dressings and diary card
- 16) Device competency assessment (completed in subject's home or equivalent. Week 4 and 8 only)

8.2.5 *Punch biopsies*

Punch biopsies may be taken at baseline and 4 weeks for up to 20 subjects enrolled in the study at selected centers. These subjects will have specifically agreed to this procedure on their Informed Consent Form.

The biopsies will be taken utilizing a standard 4 mm dermal punch biopsy kit and will be taken following routine debridement of the wounds to avoid collection of dead necrotic tissue. Prior to biopsy collection, the wound bed is prepared with local antiseptics. As per subject request, local anesthesia is administered. This is not standard because most subjects in this study will be insensate in the area of the wound.

In addition it is important to have some tissue samples without local anesthetic to determine whether the use of anesthetic agents impacts the molecular studies planned with the biopsy. Biopsies will be taken from the wound edge and from the center of the wound.

Samples will be collected, packed and transported per the procedure outlined by the testing laboratory instructions. The samples will be transported from clinic to the testing laboratory in properly secured biohazard-safe containers under appropriate temperature conditions.

The samples will be analyzed histologically for signs of infection, collagen and neo-angiogenesis. Additional immune-histochemical analyses for such values as VEG-F and matrix metalloproteinases (MMPs) are also envisioned.

8.2.6 *Premature Withdrawal of a Subject from the Trial*

Subjects are free to withdraw from the trial at any time without penalty or prejudice to their further treatment. Subjects may stop the trial treatment for any reason.

All subjects should be invited to do the End of Trial Visit to complete a final assessment, including wound status, complete quality of life questionnaire, etc.

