Subjects whose index ulcers are confirmed as closed will enter into the follow-up phase and will be terminated from further treatment with TWO2 therapy or Control therapy. Subjects will be encouraged to continue to wear the standard off-loading boot/CROW boot during the follow-up phase.

8.2.8 12 Week Follow up

All subjects will be reviewed and followed up 12 weeks after “wound closure” or the 12-week “end of treatment phase”, whichever is sooner +/- 2 weeks. Data for 12 week follow up analysis will be collected per the subject’s preference by telephone or in the clinic if attending a routine visit for wound care. Index ulcers not yet healed, will continue to be treated with best available therapy as determined by the treating medical provider.

The following assessments will be performed on all subjects:

- 1) Verify Informed Consent
- 2) Record adverse events
- 3) Record changes in concomitant medication
- 4) Quality of Life Assessment using CWIS
- 5) Pain Assessment using the Visual Numerical Rating Scale (where possible, if applicable)
- 6) Digital Photograph of the open index ulcer
- 7) Health Economic Assessment (including EQ-5D)
- 8) Education on diabetes management (and foot care/off-loading when indicated)

8.2.9 38 Week Follow up

The 38 week follow up will take place 26 weeks +/- 2 weeks from the time of the last study visit (12 week follow up). Data for 38 week follow up analysis will be collected per the subject’s preference by telephone or in the clinic if attending a routine visit for wound care. Index ulcers not yet healed, will continue with best available therapy as determined by the treating medical provider.

- 1) Verify Informed Consent
- 2) Record adverse events
- 3) Record changes in concomitant medication
- 4) Quality of Life Assessment using CWIS
- 5) Pain Assessment using the Visual Numerical Rating Scale (where possible, if applicable)
- 6) Digital Photograph of the open index ulcer (where possible)
- 7) Health Economic Assessment (including EQ-5D)
- 8) Education on diabetes management (and foot care/off-loading when indicated)
- 9) Debriefing of subjects where CWIS not previously validated

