9 STATISTICAL ANALYSIS

9.1 Sample Size and Power Analysis

All sample size estimations in this section of the protocol were undertaken using the sampsi function in Stata 11 (Statcorp LP, Texas, USA). Comparisons of groups was made assuming no continuity correction.

Little data are available on similar studies using topical oxygen therapy within randomized clinical trials making sample size estimation problematic. Large trials of dermal substitutes and negative pressure have been undertaken that can be used to indicate the potential healing in the control group. The three large trials have control healing of between 18% and 28.9% around 12 weeks after entering the trial, with a mean of 28%.^{25,27,29}

The expected improvement in healing using the active device is more problematic as there have been few comparative studies published. Aburto and Frye undertook a randomized study of 20 venous ulcers and 20 diabetic foot ulcer patients.⁴² Topical oxygen demonstrated higher healing in the DFU patients after 90 days of 90% versus 40% in the control group. Blackman et al randomized 28 patients with DFUs and obtained a similar response (82.4% versus 45.5%).²² The potential difference between treatment groups was therefore 50% and 36.9% respectively. Using these studies a total sample size of 28 and 52 would be expected based on 80% power at the 5% level of significance. Neither of these studies was blinded. It is therefore likely that the effect is likely to be substantially smaller than that experienced in these two studies.

Because of the small size of these trials and lack of blinding it has been decided to offer a more cautious approach to the calculation of sample size based on a smaller expected benefit of oxygen therapy. By combining the results of the two randomized studies already undertaken the control group achieved a healing rate of 9/21 (42.8%). In the actively treated group healing occurred in 23/27 (85.2%). Assuming an expected control rate of 43% and a difference of half that experienced in these trials of 21% (to 64%) would require a sample size of 88 patients in each group (total=176), with a power of 80% and a level of significance set at $p<0.05$.

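### The QALY difference in the cost-per-QALY ratio is not adjusted for baseline EQ-5D utility, although EQ-5D is collected at baseline; adjusting costs nothing, gains precision and removes the effect of a chance imbalance

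*Combined protocol and SAP*

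**What the plan says.** Section 7.1.2 (Economic Analysis) states: "Health utilities will be derived from the EQ-5D tool and used to calculate QALYs in each group". The incremental cost per QALY is the cost difference divided by "QALY (TWO) - QALY(control"). No covariate appears in the formula or in the text around it.

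The baseline value is available. Section 8.2.2 lists "Health Economic Assessment (including EQ-5D") among the data collected before randomised treatment, and the schedule in 8.1.1 marks the economic assessment at baseline. Section 8.2.4 repeats EQ-5D on treatment ("week 4, 8 and 12 only"), and 8.2.8 and 8.2.9 repeat it at both follow-ups.

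Section 9 has no subsection on the economic analysis. Its only economic rule, in 9.5, allows imputation of missing data. Covariate models are described for closure (9.3) and for time to closure (9.4.1, applied to recurrence in 9.4.3). Baseline utility is not named in any of them.

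**The concern.** A QALY is normally the area under a subject's utility curve from baseline onwards. Subjects who start with higher utility tend to stay higher, so an arm that happens to start higher will tend to accumulate more QALYs whatever the device does. If the analysis ignores this, part of a chance difference at baseline is read as a gain or loss from treatment.

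The QALY difference is the denominator of a ratio and is likely to be small over less than a year. A shift of the same size as the gain could double the denominator, erase it or change its sign. The cost-utility result, one of two economic ratios in the plan, could then depend on the baseline draw. The remedy uses a value that the trial already records.

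**Working it through.** **1. The plan's own figure.** Inputs from section 9.1: "Assuming an expected control rate of 43% and a difference of half that experienced in these trials of 21% (to 64"%), "with a power of 80% and a level of significance set at" 0.05, and "Comparisons of groups was made assuming no continuity correction". With n per arm = [z(alpha/2)·√(2·p̄·q̄) + z(beta)·√(p1·q1 + p2·q2)]² / 0.21² and p̄ = 0.535:
- alpha 0.05: (1.960 × 0.705 + 0.842 × 0.690)² / 0.0441 = 87.4, so 88.
- alpha 0.022 (Pocock, three looks): (2.290 × 0.705 + 0.842 × 0.690)² / 0.0441 = 109.3, so 110.

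Both figures reproduce. The documents state no QALY or EQ-5D figure to check.

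**2. Inputs for the QALY check.** From the documents: 110 per arm, a 21-point difference in closure, and a horizon from the visit schedule. Section 8.2.9 says "The 38 week follow up will take place 26 weeks +/- 2 weeks from the time of the last study visit (12 week follow up"). A subject who completes 12 weeks of treatment is therefore followed for 12 + 12 + 26 = 50 weeks, or 0.96 year. Subjects who close early reach follow-up sooner. Assumed, because the documents are silent:
- utility SD 0.20 to 0.30, taken as equal at baseline and for mean later utility;
- correlation of baseline with later utility 0.5 to 0.7;
- utility gain from a closed ulcer 0.05 to 0.15;
- about 0.9 year of accrual and about 0.8 year of benefit.

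**3. Chance baseline difference.** SE = SD × √(2/110) = SD × 0.1348, which gives 0.027, 0.034 and 0.040 at SD 0.20, 0.25 and 0.30.

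**4. What carries into the QALY difference.** Shift for a one-SE imbalance = SE × correlation × 0.9:
- low end: 0.0270 × 0.5 × 0.9 = 0.012;
- high end: 0.0405 × 0.7 × 0.9 = 0.025.

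**5. Assumed gain.** 0.21 × 0.05 × 0.8 = 0.008 to 0.21 × 0.15 × 0.8 = 0.025. The two ranges overlap almost completely.

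**6. Cross-check on the visit schedule.** With the trapezoid rule at weeks 0, 4, 8, 12, 24 and 50, the baseline value has weight 2/52 = 0.038 and later values 48/52 = 0.923. The shift is imbalance × (0.038 + 0.923 × correlation). At SD 0.25 this gives 0.017 (correlation 0.5) and 0.023 (0.7). At 0.10 utility per closed ulcer, the gain is:
- 0.21 × (6 + 38)/52 × 0.10 = 0.018 if the closure gap builds evenly to week 12 and then holds;
- 0.21 × (6 + 19)/52 × 0.10 = 0.010 if the gap closes evenly by week 50.

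The chance that the carried imbalance, in either direction, is at least as large as the gain is 29 to 44% in the first case and 55 to 66% in the second. At SD 0.20 and correlation 0.5 with the gap held it is 19%. It is near zero at SD 0.15, correlation 0.3, utility gain 0.15 to 0.20 and the gap held.

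**7. What adjustment gains.** The SE is multiplied by √(1 − r²): 0.87 at r = 0.5 and 0.71 at r = 0.7, a cut of 13 to 29%. In sample-size terms 1/(1 − r²) = 1.3 to 2.0.

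**8. What adjustment leaves.** The unadjusted SE of the QALY difference is SD × 0.9 × 0.1348 = 0.024 to 0.036. Adjusted, it is 0.024 × 0.71 = 0.017 to 0.036 × 0.87 = 0.032 (unrounded inputs). At SD 0.25 and a gain of 0.016, near the middle of the assumed range, the chance of a denominator with the wrong sign is Φ(−0.016/0.0303) = 30% unadjusted. Adjusted, it is 27% (r = 0.5) or 23% (r = 0.7).

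**9. Early stopping.** If only the 73 subjects of the first look were analysed (36.5 per arm), the baseline SE at SD 0.25 would be 0.25 × √(2/36.5) = 0.059.

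**The case against.** The strongest reply is that 7.1.2 defines a ratio and names no estimator, so an adjusted difference fits the same formula. That is right: the plan does not specify adjustment, which is different from ruling it out. Nor can one say that baseline EQ-5D would go unused, since it would enter an area under the curve as its first point. The omission still stands, because the plan names covariates where it wants them, and not here.

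Second, a reader might infer systematic bias. The documents do not support that. Section 5 describes central randomisation in permuted blocks, so the raw difference is unbiased on average, and the absence of stated stratification does not change this. What remains is error given the imbalance that actually occurs, and lost precision.

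Third, a reader might infer that an imbalance carries over in full. It carries in proportion to the correlation: about 0.50 to 0.69 QALY per unit of utility in step 6.

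Fourth, the size is one assumed range set against another. That stands, and only the textual omission is certain.

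Fifth, most of the instability survives adjustment, because the trial is small for a QALY comparison. Step 8 confirms this.

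**Conclusion.** The point holds as a free improvement to a secondary economic analysis. The plan forms the cost-per-QALY denominator without adjusting for a baseline utility that it collects. On assumed inputs that are not in the documents (SD 0.20 to 0.30, correlation 0.5 to 0.7, about 0.9 year, 110 per arm), a one-SE baseline imbalance moves the QALY difference by about 0.012 to 0.025, against an assumed gain of 0.008 to 0.025. Adjustment would cut the SE by 13 to 29%.

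Three limits apply. A reader might infer that the ratio becomes reliable once adjusted, but the wrong-sign chance falls only from about 30% to between 23% and 27% in the central case. A reader might also take cost per QALY to be a named trial objective. The synopsis names economic benefits in general, and the other ratio, cost per additional ulcer healed, does not use QALYs. Finally, pain and the Cardiff schedule are also measured at baseline, but section 9.4 gives no analysis of them to correct and no size has been worked out, so this point does not extend to them. The primary analysis and the total of 220 are unaffected.

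**What to change.** Add to section 7.1.2, or to a short economic subsection in section 9, a statement that incremental QALYs are estimated by linear regression of each subject's QALY on randomised arm and baseline EQ-5D utility. The coefficient for arm then enters the existing cost-per-QALY formula as the QALY difference. Say that baseline utility stays in the model whatever its significance, so that the stepwise elimination used in 9.3 and 9.4.1 does not apply here. Since the regression needs one QALY per subject, state in the same place how it is built from the scheduled EQ-5D assessments. Missing baseline values can be handled under the imputation that 9.5 already allows for the economic analysis.

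The cost is a few sentences and one covariate already collected, with no new visits, data or subjects. Fixing it before unblinding also prevents a choice between adjusted and unadjusted ratios once results are known.

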7.2. Safety Endpoints

This study is being conducted in North America and Europe. The study will align assessment, documentation and reporting of safety outcomes with the best available guidance that is derived from ICH GCP, ISO 14155:2011(E) and 21 CFR Part 812.

Each subject will be carefully monitored throughout the trial and asked for an account of adverse events and device effects at each study visit. An assessment must be made of the seriousness, intensity and relationship of each occurrence to the administration of TWO2 therapy or control therapy.

The subject population for this study is known to have a high incidence of morbidity and mortality. Known co-morbidities related to diabetes include cardiovascular disease, cerebrovascular disease, renal failure and deterioration of foot ulcers that may require hospitalization. The study will capture data on adverse events and device effects and serious adverse events and device effects related to the study's secondary outcome measures and will also record concomitant medication related to these occurrences. Serious adverse events that are anticipated in this population do not require expedited reporting, but they will be recorded as they may affect the status of subjects in the study. Detailed documentation of pharmaceutical interventions are not required for the safety evaluation of the device, but will be recorded where in the opinion of the PI/SubI they may directly or indirectly relate to the index ulcer.

7.2.1. **Definition of Adverse Event**

An adverse event (AE) is defined as:

An AE is: Any untoward medical occurrence, unintended disease or injury, or untoward clinical signs (including abnormal laboratory findings) in subjects, users or other persons, whether or not related to the investigational medical device

NOTE 1 This definition includes events related to the investigational medical device or the comparator.

NOTE 2 This definition includes events related to the procedures involved.

NOTE 3 For users or other persons, this definition is restricted to events related to investigational medical devices.

ISO 14155:2011E (3.2)

7.2.2. *Definition of Adverse Device Effects*

An adverse device effect (ADE) is defined as:

An adverse event related to the use of an investigational medical device.

NOTE 1 This definition includes any effect resulting from insufficiencies or inadequacies in the instructions for use or the deployment of the device.

NOTE 2 This definition includes any effect that is a result of user error (ISO 14155:2011(E) (3.1)).

7.2.3. *Definition of Unanticipated Adverse Device Effects*

An unanticipated adverse device effect (UADE) is defined as:

Unanticipated adverse device effect is any serious adverse effect on health or safety, any life-threatening problem or death caused by, or associated with a device, if that effect, problem, or death was not previously identified in nature, severity, or degree of incidence in the application; or any other unanticipated serious problem associated with a device that relates to the rights, safety, or welfare of subjects. (CFR 21 Part 812.3(s))

7.2.4. *Serious Adverse Device Effect*

A serious adverse device effect (SADE) is defined as:

Adverse device effect that has resulted in any of the consequences characteristic of a serious adverse event (ISO 14155:2011(E) (3.36)).

7.2.5. *Definition of Serious Adverse Events*

A serious adverse event (SAE) is defined as:

Any untoward medical occurrence which in any way:

- requires inpatient hospitalization or prolongation of existing hospitalization
- is life-threatening
- results in death or results in persistent or significant disability/incapacity
- is a congenital anomaly/birth defect
- or is considered serious by the investigator*

* Important medical events are those that may not be immediately life threatening, but are clearly of major clinical significance. They may jeopardize the subject, and may require intervention to prevent one of the other serious outcomes noted above.

NOTE: The term 'life-threatening,' in the definition of 'serious,' refers to an event in which the subject was at risk of death at the time of the event; it does not refer to an event which hypothetically might have caused death had it been more severe.

7.2.6. *Relationship of Events to Study Treatment*

The causal relationship of each AE to the investigational product will be assessed by the study Investigator using the following definitions:

Definite	Clear cut temporal association, and no other possible cause.
Probable	Good reasons and sufficient documentation to assume a causal relationship in the sense of plausible, conceivable, likely but not necessarily highly probable.
Possible	Sufficient information to accept the possibility of a causal relationship in the sense of not impossible and not unlikely, although the connection is uncertain or doubtful, e.g. due to missing data or

None	insufficient evidence. The AE is completely independent of the trial product administration and/or evidence exists that the event is definitely related to another etiology.
------	---

